#### **8.5** ECOG Performance Status

For the purpose of evaluating safety, ECOG will be summarized as shift from baseline tables for, at minimum, the worst value recorded after the initiation of study treatment. Only results with assessment dates through the end of the safety observation period (see section 4.5) will be tabulated in summary tables.

Frequencies of ECOG worsening of  $\geq +1$  and +2 change from baseline to worst value after first dose will also be summarized.

# 8.6 Electrocardiogram (ECG)

Only results with assessment dates through the end of the safety observation period (see section 4.5) will be considered for summaries. The following categorical summaries will be presented per investigator and per independent review:

- number of subjects with triplicate average QTc > 500 ms after first dose
- number of subjects with increase in triplicate average QTc from baseline of >60ms
- number of subjects with increase in triplicate average QTc from baseline of >30ms after first dose

For the above summaries, the most-recent average value from triplicate measurements taken before first dose will be used as baseline. If no triplicate measurements were taken before first dose, the most-recent single value taken before first dose will be used as baseline.

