### **5.7.4 Electrocardiograms**

Standard 12-lead equipment will be used for all ECGs. The Fridericia formula is depicted below for calculation of the corrected QT interval (QTcF).

$$QTcF = \frac{QT}{RR^{1/3}}$$

QT = measured QT interval in milliseconds; RR = measured R to R interval (which can be derived from the heart rate as 60/heart rate)

ECGs to establish eligibility must be done within 7 days prior to randomization (Appendix A [Appendix B for the Open-Label Phase]). To confirm suitability for treatment after randomization, ECGs must be repeated on W1D1 prior to administering the first dose of study treatment unless the screening tests were performed within 10 days prior to W1D1.

At screening, if the initial QTcF is > 500 ms, a total of 3 ECGs each separated by at least 3 minutes should be performed. If the average of the 3 results for QTcF is ≤ 500 ms, the subject is eligible for the study.

During the study, single ECG assessments will be performed as indicated in Appendix A. If cardiac abnormalities are detected or suspected, two additional ECGs must be performed at intervals at least 3 minutes apart in order to confirm the finding. If at any time while on study there is an increase in average QTcF >500 ms, study treatment must be immediately interrupted and instructions in Section 6.7.10 for continued monitoring of QTc must be followed.

Abnormalities in the ECG that lead to a change in subject management (eg, dose reduction or delay, treatment discontinued, requirement for additional medication or monitoring) or that result in clinical symptoms are considered clinically significant for the purposes of this study and should be reported as AEs by the Investigator. If values meet criteria defining them as serious, they must be reported as SAEs (Section 8.2).

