### 6.7.10 Corrected QTc Prolongation

The effect of orally administered cabozantinib at 140 mg/day (FBE) on QTc interval was evaluated in a randomized, double-blinded, placebo-controlled Phase 3 study in patients with MTC (Study XL184-301). A mean increase in QT interval corrected by Fridericia (QTcF) of 10-15 ms was observed at 4 weeks after initiating cabozantinib. A concentration-QTc relationship could not be definitively established. Changes in cardiac wave form morphology or new rhythms were not observed. No cabozantinib treated patients on this study had a QTcF > 500 ms during the QT evaluation period.

Only subjects with a baseline QTcF ≤ 500 ms are eligible for this study. Subjects will have ECGs performed at times designated by the protocol (Section 5.2).

If at any time on study there is an increase in QTcF interval to an absolute value > 500 ms, within 30 minutes after the initial ECG, 2 additional ECGs must be performed each with intervals approximately 3 minutes apart.

If the average QTcF from the 3 ECGs is  $> 500$  ms, the following actions must be taken:

- Withhold study treatment
- Immediately notify the Sponsor
- Hospitalize symptomatic subjects (eg, with palpitations, dizziness, syncope, orthostatic hypotension, a significant ventricular arrhythmia on ECG) for a thorough cardiology evaluation and management
- Consider cardiology consultation for asymptomatic subjects for evaluation and management
- Check electrolytes, especially magnesium and potassium; correct abnormalities as clinically indicated
- Check concomitant medications for any medication that may have contributed to QT prolongation, and if possible, discontinue these medications (see <http://www.qtdrugs.org>)
- Send ECGs to central ECG laboratory (see ECG study manual)
- Repeat ECG triplicates hourly until the average QTcF is  $\leq 500$  ms

Study treatment may be restarted at a reduced dose level if all of the following conditions are met:

- Symptoms are determined to be unrelated to the QT interval prolongation
- The QTcF value  $> 500$  ms is not confirmed by the central ECG laboratory or a QTcF  $> 500$  ms confirmed by the central laboratory returns to  $\leq 500$  ms
- Study treatment has been interrupted through a minimum of 1 week following the return of the QTcF to  $\leq 500$  ms
- Sponsor has reviewed all available information and has agreed to the continuation of study treatment

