Physical exam (PE) + weight (Section 5.7.2)	≤ 7 d (with height)	X (prior to first dose; symptom-directed PE)	X	X	X	X	Every 4 wks (W13D1, W17D1 etc)	X	
Vital signs (Section 5.7.3)	≤ 7 d	X (prior to first dose)	X	X	X	X	Every 4 wks (W13D1, W17D1 etc)	X	
ECOG (Appendix D: ECOG Performance Scale)	≤ 7 d	X (prior to first dose)	X	X	X	X	Every 4 wks (W13D1, W17D1 etc)	X	
12-lead ECG with QTc (Section 5.7.4) c	≤ 7 d	X (prior to first dose) d	X	X		X		X	
Hematology by central lab (Section 5.7.5) e	≤ 7 d	X (prior to first dose) d	X	X	X	X	Every 4 wks (W13D1, W17D1 etc)	X	
Serum chemistry by central lab (Section 5.7.5) e	≤ 7 d	X (prior to first dose) d	X	X	X	X	Every 4 wks (W13D1, W17D1 etc)	X	
Coagulation panel by central lab (Section 5.7.5) e	≤ 7 d	X (prior to first dose) d	X	X	X	X	Every 4 wks (W13D1, W17D1 etc)	X	
UPCR by central lab (Section 5.7.5) e	≤ 7 d	X (prior to first dose) d	X	X	X	X	Every 4 wks (W13D1, W17D1 etc)	X	

	Pre-randomization	Post-randomization							
	Screening (before randomization) a	W1D1 (≤ 3d after randomization)	W3D1 (±3 d)	W5D1 (±3 d)	W7D1 (±3 d)	W9D1 (±3 d)	Beyond Week 9 (±5 d)	30-day Post-Treatment Follow-Up (+14 d)	Extended Follow-Up
Fasting serum glucose by local lab (only if HbA1c result is unavailable; Section 5.7.5)	≤ 28 d								
Urinalysis by local lab (Section 5.7.5) e	≤ 7 d					X	Every 8 wks (W17D1, W25D1 etc)	X	
Serum pregnancy test by local lab (Section 5.7.5) e	≤ 7 d	X (prior to first dose) d		X		X	Every 4 wks (W13D1, W17D1 etc)	X	
Thyroid function panel by central lab (Section 5.7.5) e	≤ 28 d	X (prior to first dose) d				X	Every 8 wks (W17D1, W25D1 etc)	X	
AFP by central lab (Section 5.7.7) e	≤ 28 d	AFP every 8 weeks (± 5 d) after randomization (W9D1, W17D1 etc). Assessments should continue regardless of whether study treatment is given, reduced, interrupted, or discontinued until the later of 8 weeks after radiographic progression per RECIST 1.1 as determined by the investigator or the date of the decision to permanently discontinue study treatment							

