# 8.3.2 Analysis

All laboratory data parameters and visits will include flags for values above or below laboratory reference ranges. Toxicity grades will be assigned programmatically by applying the CTCAE v4 guidelines. Only results with assessment dates through the end of the safety observation period (see section 4.5) will be tabulated in summary tables.

Laboratory summaries will be presented in SI units. Continuous laboratory test results will be summarized by treatment group using descriptive statistics for actual values and for changes from baseline by scheduled visit. Box-Whiskers plots may also be presented at each scheduled visit (with visits shown on x-axis) for some laboratory parameters. For continuous laboratory test results which are below or above the quantification level, the imputed values as described in Appendix C will be used for deriving the grade and then summarized.

Tables summarizing the incidence of laboratory abnormalities by maximum post-baseline CTCAE grade overall and by baseline grade will be presented. In addition, the following summaries will also be presented:

AlLiver function abnormalities will be assessed as follows:

- Shift from baseline based on normal ranges
- Summaries of subjects meeting Hy's Law laboratory screening criteria as shown below:

```
    >3× ULN (ALT or AST), >2× ULN Total Bilirubin, and <2× ULN ALP

    >3× ULN (ALT or AST), >2× ULN Total Bilirubin, and ≥2× ULN ALP
```

- Sponsor-defined liver function test surveillance criterion:
  - >10× ULN (ALT or AST) and >2× ULN Total Bilirubin
- B] For renal failure surveillance, a summary of subjects meeting renal failure laboratory screening criteria as shown below will be provided:
  - Serum creatinine >= 3.0xULN and >= 2.0x baseline value or
  - eGFR  $\leq$  50% of the baseline value or

- eGFR < 30 mL/min/1.73 m² and ≥ 25% reduction from the baseline value eGFR = 186 x (Creatinine in mmol per L / 88.4)-1.154 x (Age)-0.203 x (0.742 if female) x (1.210 if black) [from the UK CKD eGuide on the Renal Association website: http://egfrcalc.renal.org/]
- C] Categorical summaries for baseline status for TSH and Free T4 will be presented. In addition categorical summaries for post-baseline TSH and Free T4 status among subjects with TSH and Free T4 in the normal range at baseline will also be presented.

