# 8.4.2 Analysis

Summary tables of vital signs and change from baseline for each study visit will be presented. Only results with assessment dates through the end of the safety observation period (see section 4.5) will be considered for the summaries.

Subject-incidence of clinically meaningful vital sign results as shown below will also be presented:

- Subjects who got worse since baseline and met the following blood pressure criteria on 2 or more visits (need not be consecutive) after first dose (JNC criteria were modified to include single measurement per time point when triplicate assessments were unavailable; JAMA 2003:289:2560):
  - o Pre-hypertension: SBP 120-139 mmHg or DBP 80-89 mmHg
  - Stage 1: SBP 140-159 mmHg or DBP 90-99 mmHg
  - $\circ$  Stage 2: (SBP >= 160 mmHg and DBP <120) or DBP 100-119 mmHg
  - $\circ$  Stage 3: DBP >= 120 mmHg
- Proportion of subjects with weight loss  $\geq 10\%$  after first dose

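### SAP 8.6 counts QTc rises of >30 and >60 ms only on triplicate averages although scheduled on-study ECGs are single; the SAP's UPCR cut-point for 1.0 mg/mg is also mis-converted

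*SAP*

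**What the plan says.** **QTc.** SAP 8.6 lists three categorical summaries: QTc above 500 ms, a rise above 60 ms and a rise above 30 ms. All are built on the triplicate average; the second reads "number of subjects with increase in triplicate average QTc from baseline of >60ms". A fallback exists for the baseline value only: "If no triplicate measurements were taken before first dose, the most-recent single value taken before first dose will be used as baseline". Nothing equivalent is given for post-dose values.

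Protocol 5.7.4 sets the data collection: "During the study, single ECG assessments will be performed as indicated in Appendix A". It continues: "If cardiac abnormalities are detected or suspected, two additional ECGs must be performed". Protocol 6.7.10 separately requires two further ECGs when QTcF goes above 500 ms in absolute terms. The Appendix A row "12-lead ECG with QTc (Section 5.7.4") schedules post-dose ECGs at W3D1, W5D1, W9D1 and the 30-day post-treatment visit. Protocol 9.7.3 promises a by-arm summary of QTc changes or shifts from baseline, with no restriction to triplicates.

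**UPCR.** SAP 8.3.1 gives sponsor-defined grades with cut-points of 0.15, 1.0 and 3.5 mg/mg, shown as 17.0, 121.0 and 396.0 mg/mmol. Protocol inclusion criterion 9b and Table 6-7 equate 1 mg/mg with 113.1 mg/mmol. SAP 8.3.2 states: "Laboratory summaries will be presented in SI units".

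**BMI.** SAP 5.3 multiplies weight in kg by 1000 and divides by the square of height in cm.

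**The concern.** The analysis rule does not match the data the protocol collects. Most post-dose ECGs will be single readings, so they have no triplicate average. SAP 4.4 rules out imputing missing data other than partial dates, so such visits drop out of the counts. What remains depends partly on whether someone judged the tracing abnormal and had it repeated, not only on whether QTc rose.

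The >30 and >60 ms categories are where a signal would be expected. Protocol 6.7.10 reports, from an earlier study at 140 mg/day: "A mean increase in QT interval corrected by Fridericia (QTcF) of 10-15 ms was observed at 4 weeks", with no treated patient above 500 ms during the evaluation period. SAP 8.6 is the SAP's only QTc summary, so no other table would recover the missed rises.

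The UPCR slip would put some proteinuria just above 1 mg/mg in the wrong grade. The BMI slip would make one descriptive row wrong by a factor of ten.

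**Working it through.** **1. Which rises can reach the QTc counts**

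| Situation after first dose | Repeat ECGs required? | Enters SAP 8.6 counts? |
|---|---|---|
| Scheduled single ECG, no abnormality suspected, QTcF at or below 500 ms | No | No |
| Abnormality detected or suspected (Protocol 5.7.4) | Yes, two more | Yes |
| QTcF above 500 ms (Protocol 6.7.10) | Yes, two more | Yes |

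No rule ties a repeat to a change from baseline. The largest rise that avoids the 500 ms trigger is 500 minus baseline:

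- baseline 400 ms: 500 - 400 = 100 ms
- baseline 420 ms: 500 - 420 = 80 ms
- baseline 440 ms: 500 - 440 = 60 ms

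Example: 485 - 420 = 65 ms. This exceeds both thresholds, stays below 500 ms and compels no repeat under 6.7.10.

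**2. How many rises the rule could touch (illustration)**

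Inputs: 507 cabozantinib subjects (Protocol 9.9) and a normal distribution for the change at one visit. The documents give a mean rise of 10-15 ms at 140 mg/day; a mean down to 5 ms is assumed here for the 60 mg dose. The SD of 15-20 ms is an assumption, since the documents give none. P(change > c) = 1 - Φ((c - mean)/SD).

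| Mean, SD (ms) | Threshold c (ms) | (c - mean)/SD | Probability | Of 507 |
|---|---|---|---|---|
| 5, 15 | 30 | 1.67 | 4.8% | 24 |
| 10, 15 | 30 | 1.33 | 9.1% | 46 |
| 10, 20 | 30 | 1.00 | 15.9% | 80 |
| 15, 20 | 30 | 0.75 | 22.7% | 115 |
| 5, 15 | 60 | 3.67 | 0.01% | 0.1 |
| 15, 20 | 60 | 2.25 | 1.2% | 6.2 |

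These are subjects with a rise at one visit, not subjects lost.

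A second illustration asks what share of such rises would stay at or below 500 ms and so escape the mandatory repeat. By simulation, with baseline mean 410-430 ms and SD 20, and change mean 12.5 ms and SD 15-25 (all assumed), the share is about 86-99% of rises above 30 ms and 51-89% of rises above 60 ms.

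**3. UPCR conversion**

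Factor from the protocol: 1 mg/mg = 113.1 mg/mmol.

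| mg/mg | SAP, mg/mmol | mg/mg × 113.1 | Factor implied by SAP | Reproduces? |
|---|---|---|---|---|
| 0.15 | 17.0 | 16.97 | 17.0/0.15 = 113.3 | Yes |
| 1.0 | 121.0 | 113.1 | 121.0/1.0 = 121.0 | No, 7.0% too high |
| 3.5 | 396.0 | 395.85 | 396.0/3.5 = 113.1 | Yes |

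Back-conversion: 121.0/113.1 = 1.07 mg/mg. Values above 113.1 and below 121.0 mg/mmol (1.00-1.07 mg/mg) are Grade 2 in mg/mg but Grade 1 in SI units.

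**4. BMI**

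For 70 kg and 170 cm, the SAP formula gives 70 × 1000/170² = 2.42. With 10,000 it gives 70 × 10,000/170² = 24.2.

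**The case against.** Requiring a triplicate average can be defended as a confirmation rule, because single ECGs are noisy. With the SDs assumed above and no true change, the chance of exceeding 30 ms at one visit is 2.3% (30/15 = 2.0) to 6.7% (30/20 = 1.5), about 6-17 of 253 placebo subjects. Counting single readings would admit such rises. This stands as a cost of the remedy. It does not justify the present rule: the SAP gives no confirmation rationale, and the rule makes most scheduled ECGs unusable.

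SAP 8.4.2 adapts its blood pressure criteria "to include single measurement per time point when triplicate assessments were unavailable", which looks like a precedent. It also requires the criterion to be met on at least two visits, so the parallel is partial. It does show that the SAP foresaw missing triplicates in one section and not in the other.

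Repeating is mandatory once an abnormality is suspected, so the discretion lies in judging what is abnormal. The documents do not say whether a 60 ms rise would count, and the ECG manual is not available. Clinically significant ECG abnormalities are also reported as adverse events. These points limit the loss but leave the counts dependent on that judgement.

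For UPCR, the mg/mg cut-point is printed beside the SI one, and no text says which will be programmed. The two still contradict each other, and reporting is in SI units.

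**Conclusion.** The concern holds on all three items.

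- **QTc.** As written, a rise above 30 or 60 ms seen only on a scheduled single ECG cannot be counted, so both counts will tend to be too low. The size of the shortfall is unknown because the number of repeated ECGs cannot be derived. The ranges of 24-115 subjects (>30 ms) and about 0-6 subjects (>60 ms) out of 507 rest on an assumed mean and SD and show only how many rises the rule could touch at one visit. The >500 ms count is largely protected by the mandatory repeats.
- **UPCR.** The 1.0 mg/mg cut-point is 7.0% too high in SI units. The affected band is narrow, and the Grade 3 cut-point is unaffected.
- **BMI.** A constant is wrong by a factor of ten in one baseline row.

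All of this concerns descriptive tables. OS, PFS, ORR, alpha and power are untouched. The QTc rule is the item that should be changed; the other two are corrections to make at the same time.

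**What to change.** 1. In SAP 8.6, state that each post-dose time point uses the triplicate average where one exists and otherwise the single value. Report how many counted subjects rest on a single value only, so that readers can see the contribution of unconfirmed readings.
2. In SAP 8.3.1, replace 121.0 by 113.1 mg/mmol in the Grade 1 and Grade 2 lines for UPCR.
3. In SAP 5.3, replace 1000 by 10,000 in the BMI formula.

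These are text and programming edits. They need no new data and change no ECG schedule, monitoring rule or dosing rule. SAP 4.8 provides for a revised version or an addendum approved before unblinding. The price of the first change is some noise-driven rises in both arms, which the separate reporting makes visible.

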#### 9 IDENTIFICATION AND SUMMARY OF PROTOCOL DEVIATIONS

In accordance with ICH E3, important eligibility deviations per the inclusion/exclusion criteria and important post-randomization protocol deviations tracked in CTMS (clinical trial management system) will be identified and listed separately by study center and subject. Important deviations will be summarized for the ITT population as follows:

#### Deviation code:

- DID NOT SATISFY INCLUSION OR EXCLUSION CRITERIA
- PROHIBITED MEDICATION
- TREATMENT DEVIATION
- WITHDRAWAL DEVIATION
- RANDOMIZATION IRREGULARITY
- OTHER PROTOCOL DEVIATION

# Deviations category:

- IMPORTANT
- OTHER

## Deviations sub-category:

- POTENTIALLY IMPACTING SAFETY
- POTENTIALLY IMPACTING EFFICACY
- POTENTIALLY IMPACTING SAFETY AND EFFICACY
- OTHER

# 10 DATA QUALITY ASSURANCE

The Clinical, Data Management, Biostatistics, and Medical Writing departments at Exelixis and designees will work diligently and collaboratively to ensure that the data collected and analyzed for this study are of the high quality. In addition to electronic evaluation of the data and verification of data from source documents at the respective sites, a data review meeting will be held to review the data and correct significant data anomalies before the study database is locked or data are extracted for the purpose of analysis.

# **Appendix A: Date Imputation Rules**

## Incomplete Cancer Diagnosis Date

If year is missing (or completely missing): do not impute

If only *day* is missing: set to 15th of the month.

If day and month are missing: set to July 1st.

If either imputation rule above results in a diagnosis date > informed consent:

set diagnosis date to the date of informed consent - 1.

## Incomplete Adverse Event Onset Date

Assumption: For on-study Adverse Events.

If year is missing (or completely missing): set to the date of first dose.

If (year is present and month and day are missing) or (year and day are present and month is missing):

If *year* = year of first dose: set the date to the first dose date.

If year < year of first dose: set month and day to December 31st.

If year > year of first dose: set month and day to January  $1^{st}$ .

If *month* and *year* are present and *day* is missing:

If year = year of first dose, and:

If *month* = month of first dose: set *day* to day of first dose.

If *month* < month of first dose: set *day* to last day of *month*.

If month > month of first dose: set day to  $1^{st}$  day of month.

If *year* < year of first dose: set *day* to last day of month.

If year > year of first dose: set day to 1st day of month.

For all other cases: set to date of first dose.

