## 8 SAFETY

### 8.1 Adverse Events and Laboratory Abnormalities

An AE is any untoward medical occurrence in a patient or clinical investigation subject who has been enrolled in a clinical study and who may have been administered an investigational product, regardless of whether or not the event is assessed as related to the study treatment. An AE can therefore be any unfavorable and unintended sign (including an abnormal laboratory finding), symptom, or disease temporally associated with the use of an investigational product, regardless of whether or not the event is assessed as related to the investigational product. This definition also includes events associated with medication errors and uses of the investigational product outside of what is in the protocol, including misuse and abuse. Preexisting medical conditions that worsen during a study should be recorded as AEs. Abnormal laboratory values, ECG findings, or vital signs are to be recorded as AEs if they meet the criteria described in Section 8.3.

All untoward events that occur after informed consent through 30 days after the date of the decision to discontinue study treatment are to be recorded by the investigational site. At each scheduled and unscheduled visit, AEs are to be identified and assessed based upon study procedures, routine and symptom-directed clinical investigations, and subject query/report.

Assessment of the relationship of the AE to the study treatment by the investigator will be based on the following two definitions:

- **Not Related**: An event is assessed as not related to study treatment if it is attributable to another cause and/or if there is no evidence to support a causal relationship.
- **Related**: An event is assessed as related to study treatment when there is a reasonable possibility that the study treatment caused the event. Reasonable possibility means there is evidence to suggest a causal relationship between the drug and the event. This event is called a suspected adverse reaction. A suspected adverse reaction implies a lesser degree of certainty about causality than adverse reaction, which means any adverse event caused by a drug.

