#### 8.1 Adverse Events

Adverse event terms recorded on the CRF will be mapped to preferred terms and system organ class using the Medical Dictionary for Regulatory Activities (MedDRA). The severity of AEs will be measured by CTCAE (Cancer Therapy Evaluation Program 2009) version 4 guidelines. The investigator will judge each event to be "not related" or "related" to study treatment.

A TEAE is defined as any event with an onset date on or after the date of the first dose of study drug or any ongoing event on the date of the first dose of study drug that worsens in severity after the date of the first dose of study drug.

Only TEAEs with an onset date through the end of the safety observation period (see section 4.5) will be tabulated in summary tables.

For the purpose of calculating treatment emergence and inclusion in summary tables, incomplete onset dates will be imputed as detailed in Appendix A.

For AE reporting, percentages  $\geq 10\%$  will generally be presented as integers, those  $\leq 10\%$ 

will be presented with 1 decimal place (e.g. X.X%). Rounding rules are provided in Appendix B. The calculations of percentages will be based on original unrounded values.

An overall summary of adverse events will be provided with the number and percent of subjects who experienced the following types of events during the safety observation period (unless otherwise noted) in each treatment arm:

- Subjects with a TEAE
- Subjects with a Related TEAE
- Subjects with a Serious TEAE
- Subjects with a Serious Related TEAE at any time
- Subjects with a Worst-Grade 3 or 4 TEAE
- Subjects with a Worst-Grade 3 or 4 Related TEAE
- Subjects with a Worst-Grade 4 TEAE
- Subjects with a Worst-Grade 4 Related TEAE
- Subjects with a Grade 5 TEAE at any time
- Subjects with a Grade 5 TEAE
- Subjects with a Grade 5 TEAE through 30 days after the last dose of the study treatment
- Subjects with a Grade 5 AE judged not to be causally related to PD through 30 days of last dose of the study treatment
- Subjects with a Grade 5 AE >30 days after the last dose of the study treatment
- Subjects with a Grade 5 AE judged not to be causally related to PD >30 days of last dose of the study treatment
- Subjects with a Related Grade 5 TEAE at any time
- Subjects with a Related Grade 5 TEAE
- All subjects who died
- Subjects who died within 30 days after date of last dose of study treatment
- Subjects with a TEAE leading to Dose Modification

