Macrovascular Invasion per	(descending frequency of Gr3/4 in the	All Grades, Grade 3/4, Grade 4, Grade 5
Cancer History CRF	cabo arm)	
All SAEs for Subjects without	PT	Worst severity:
Macrovascular Invasion per	(descending frequency of Gr3/4 in the	All Grades, Grade 3/4, Grade 4, Grade 5
Cancer History CRF	cabo arm)	

The following data listings will also be provided with indicators for grade, relationship, seriousness, dose day of the event start/stop, days since last dose, action taken with study treatment:

- All AEs
- Grade 5 AEs
- Serious AEs other than death

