#### Incomplete Subsequent Anti-Cancer Therapy Start Date

Assumption: Anti-Cancer therapies reported on the Subsequent Anti-Cancer Therapy CRF. If *year* is missing (or completely missing): set to date of last dose of study treatment + 1 If (*year* is present and *month* and *day* are missing) or (*year* and *day* are present and *month* is missing):

If year > year of the last dose: Set *month* and day to January 1st.

If year = year of the last dose: Set month and day to date of last dose of study treatment + 1 If year and month are present and day is missing:

Set *day* to 1st day of month if the resulting imputed date is greater than date of last dose or if the month is before the month of last dose date and year is same or before the year of the last dose date. Otherwise set the imputed date to date of last dose + 1

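### Two date rules in SAP Appendix A can override recorded dates: the adverse event onset rule ignores the stop date, and the subsequent-therapy rule compares month and year separately

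*SAP*

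**What the plan says.** **AE onset (SAP Appendix A, Incomplete Adverse Event Onset Date).** The onset becomes the first-dose date in three situations:

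- the year is unknown: "If year is missing (or completely missing): set to the date of first dose";
- the month is unknown and the year matches: "year of first dose: set the date to the first dose date";
- month and year are known and both equal those of first dose.

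A catch-all follows: "For all other cases: set to date of first dose". Other branches place the onset before first dose when the recorded year or month is earlier. The rule opens with "Assumption: For on-study Adverse Events", a term the SAP does not define. No branch refers to the AE stop date.

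SAP 8.1 gives these dates their force: "For the purpose of calculating treatment emergence and inclusion in summary tables, incomplete onset dates will be imputed as detailed in Appendix A". It defines a treatment-emergent AE (TEAE) by onset on or after first dose, or by worsening after first dose of an event ongoing at that time. Stop dates exist, because the AE listings are to show "dose day of the event start/stop". Protocol 8.1 requires sites to record "All untoward events that occur after informed consent", and Protocol 6.5.1 starts AE monitoring at the signing of consent.

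**Subsequent therapy start (SAP Appendix A, Incomplete Subsequent Anti-Cancer Therapy Start Date).** When only the day is missing, the 1st of the recorded month is used in two cases. One is that this date is later than last dose; the other reads "if the month is before the month of last dose date and year is same or before the year of the last dose date". In every remaining case the start becomes the day after last dose. When the month is missing there are rules for a year equal to or later than the last-dose year, and none for an earlier year.

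**The concern.** Imputation should fill what is unknown without contradicting what is known. Elsewhere Appendix A respects this. An imputed cancer diagnosis date is held before consent, a death date is bounded by the date last known alive, and dosing dates are bounded by the neighbouring dosing milestones. The two rules here lack such a check.

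For AEs, an event that was over before any study drug was taken can enter the TEAE tables of either arm.

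For therapy, the start date drives several efficacy derivations:

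- PFS1 and PFS3 censoring (SAP 7.2.1.1 and Table 3);
- the PFS2 event date (Table 3);
- best overall response and hence ORR, which stop at the PFS censoring events (SAP 7.2.2.1);
- the exploratory OS analysis censored at other therapy (SAP 7.1.4).

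PFS and ORR are formally tested, so a start date that contradicts the recorded month matters in principle.

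**Working it through.** The plan states no figure to reproduce. The check applies each rule as written to test dates; all dates below are assumed for illustration.

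**1. AE onset rule.** First dose 20 March 2015; AE stop date 10 March 2015.

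| Recorded onset | Imputed onset | Counted as TEAE |
|---|---|---|
| nothing | 20 March 2015 | yes |
| 2015 only | 20 March 2015 | yes |
| March 2015 | 20 March 2015 | yes |
| February 2015 | 28 February 2015 | no |
| 2014 only | 31 December 2014 | no |

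In the first three rows the imputed onset is 20 − 10 = 10 days after the event ended. Capping the onset at the stop date gives 10 March 2015 in those rows, and the event is no longer a TEAE. The last two rows are already right and do not change.

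**2. Therapy start rule.** The rule keeps the 1st of the recorded month if that date is after last dose, or if the month is before the last-dose month and the year is the same or earlier. The second condition can be read in two ways: by calendar month number (literal), or by month and year together.

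| Recorded start | Last dose | Literal reading | Month-and-year reading |
|---|---|---|---|
| January 2016 | 10 March 2016 | 1 January 2016 | 1 January 2016 |
| November 2015 | 10 March 2016 | 11 March 2016 | 1 November 2015 |
| March 2015 | 10 March 2016 | 11 March 2016 | 1 March 2015 |
| February 2015 | 10 March 2016 | 1 February 2015 | 1 February 2015 |
| December 2015 | 31 December 2015 | 1 January 2016 | 1 January 2016 |

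Under the literal reading February 2015 is kept while the more recent November 2015 is moved forward. For November 2015 the error is at least 31 + 31 + 29 + 11 = 102 days, counted from 30 November 2015 to 11 March 2016. For March 2015 it is at least 366 − 20 = 346 days, counted from 31 March 2015.

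**3. All last-dose dates in 2016.** Each of the 366 dates was paired with the last-dose month and the 12 months before it, giving 366 × 13 = 4,758 combinations. Of these, 2,374 have a recorded month in the prior year.

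- Literal reading: all 2,374 move into the later year. So does one more, a December start with last dose on 31 December.
- Month-and-year reading: 12 combinations leave their recorded month, one per month end, and 1 of these enters the next year.

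These counts describe the logic, not subjects.

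**4. Consequence for PFS1.** Take therapy recorded as November 2015, last dose 10 March 2016 and radiographic progression on 20 January 2016. With the recorded month, the subject is censored at the last adequate tumor assessment on or before 1 November 2015. With the literal imputed start of 11 March 2016, progression precedes the therapy and counts as a PFS1 event, provided no other censoring rule applies.

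**The case against.** **AE rule.** Setting an unknown onset to first dose is an ordinary conservative choice that over-counts rather than hides TEAEs. That stands wherever nothing contradicts it; the gap is only the missing check against a known stop date.

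The label on-study could be taken to mean after first dose. The rule's own branches for a year or month before first dose, and the start of AE monitoring at consent in Protocol 6.5.1, speak against that.

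It is less certain how many pre-dose events reach the analysed data. SAP 8.1 analyses terms recorded on the CRF. Protocol 8.2.1 requires entry on the AE CRF page for SAEs occurring after study treatment begins, and Protocol 5.7.2 puts pre-dose intercurrent conditions on a CRF without naming which one. This part of the objection stands and limits the size.

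**Therapy rule.** The first branch works properly in the usual case, where therapy starts in a month after last dose. Protocol 7.1.2 requires study treatment to stop when other systemic or liver-directed therapy is needed, so starts before last dose should be rare. The large error also depends on the literal reading. All of this stands. The month-end case and the missing year-only rule remain under either reading.

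**Stronger inferences that the documents do not support.**

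- A reader might infer that the TEAE comparison is materially diluted. The documents give no rate of pre-dose AEs, of partial onset dates or of events already ended. Protocol 9.7.1 counts each preferred term once per subject, so a later on-treatment episode would count that subject anyway. No formal safety comparison is planned.
- A reader might infer that impossible AE durations distort the tables. SAP 8.1 summarises subject incidence, and no AE duration table is planned.
- A reader might put a 12-month ceiling on the therapy date error. The literal rule sets none: December 2014 with last dose 10 March 2016 also becomes 11 March 2016, at least 365 + 31 + 29 + 11 = 436 days late.

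**Conclusion.** Both rules, as written, can produce dates that contradict recorded data, and both deserve correction. This is a minor point.

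The AE error needs an onset incomplete in one of the three listed ways, a known stop date before first dose, and an event that is on the analysed CRF. The number of subjects cannot be derived from the documents; a handful at most is a judgement, not a calculation.

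The large therapy error needs three things: the literal reading, a missing day, and a start in an earlier calendar year than last dose with a month number equal to or later than the last-dose month. To alter PFS1 it also needs progression or death between the true and imputed dates. Under the month-and-year reading only the month-end shift is left. Few subjects should be affected either way.

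A reader might infer a threat to the trial's main conclusion. There is none: the primary OS analysis uses neither date.

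**What to change.** Amend Appendix A as follows.

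1. **AE onset.** If a complete AE stop date is before first dose, set the imputed onset to the earlier of the rule's date and the stop date, and do not count the event as treatment-emergent. If the stop date is partial, apply this only when its latest possible date is before first dose, using that latest date as the cap.
2. **Therapy start, day missing.** Keep the existing branch for a recorded month whose 1st is after last dose. Otherwise compare year and month together. If they are earlier than those of last dose, use the 1st of the recorded month. If they are the same, use the day after last dose, but no later than the last day of the recorded month.
3. **Therapy start, only the year known and earlier than the last-dose year.** Add a rule that keeps the imputed date within the recorded year, and name the day to be used.

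On the test dates, the March 2015 onset becomes 10 March 2015, the November 2015 start becomes 1 November 2015, and the December 2015 start with last dose on 31 December stays in December.

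The cost is a few sentences and the matching program conditions. SAP 4.8 allows clarifications and minor corrections by addendum before unblinding. No new data are needed.
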